Comparison of Effects of Peripheral Nerve Block and Topiramate in the Treatment of Medication Overuse Headaches

07.07.2019

Purpose

In this study, we compared the effectiveness of peripheral nerve block (greater occipital nerve block with supraorbital nerve block) versus topiramate as detoxification therapies in chronic migraine patients with medication overuse headache.

Methods

Ninety chronic migraine patients with medication overuse headache were included in this study. Patients divided into the two groups. The first group received topiramate and the second group received nerve block as detoxification therapy. Patients' records regarding the VAS scores and headache frequencies were collected before and after the therapy. Comparisons regarding VAS scores, headache frequencies, 50% responder rates and 75% responder rates were performed in between topiramate and nerve block groups.

Data collection

The study was carried on by 2 neurologists. The first neurologist obtained the data regarding the migraine features from each patient included. Each patient kept a diary documenting frequency, visual analog scale (VAS) as the number of headache attacks in the preceding 4 weeks. At the end of the fourth week, forms were collected by first neurologist and patients were referred the second neurologist for treatment regimens were to be introduced. Detoxification process was maintained in the inpatient clinic for ten days and preventive treatment was started simultaneously by

the second neurologist. After discharge, new forms were delivered and collected by the first neurologist after 4 weeks. All patients were informed about possible adverse reactions and those caused discontinuation of therapy were noted.

Statistical analysis

Normality of distribution was assessed with the D'Agostino-Pearson test. Continuous variables with a normal distribution were assessed in two or more groups using the Student's t-test. Mann Whitney U was utilized to compare the data that were not normally distributed. Nominal categorical data were assessed using the chisquare test. The pre- and post-treatment comparison of normally and non-normally distributed data were undertaken using the paired t-test and the Wilcoxon test, respectively. A two-tailed p value of <0.05 was considered statistically significant.

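### Only adverse reactions that stopped therapy are described as recorded, so the data as described cannot support a comparison of tolerability between topiramate and nerve block

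*Combined protocol and SAP*

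**What the plan says.** All of the following is in the combined protocol and SAP, which is short.

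- **Harms (Data collection).** One sentence: "All patients were informed about possible adverse reactions and those caused discontinuation of therapy were noted". It covers all patients, with no separate rule for either arm.
- **Diary (Data collection).** "Each patient kept a diary documenting frequency, visual analog scale (VAS) as the number of headache attacks in the preceding 4 weeks".
- **Before and after treatment (Methods).** Patients' "records regarding the VAS scores and headache frequencies were collected before and after the therapy".
- **Follow-up (Data collection).** "Detoxification process was maintained in the inpatient clinic for ten days", with preventive treatment started at the same time by the second neurologist. Then: "After discharge, new forms were delivered and collected by the first neurologist after 4 weeks". The items on these new forms are not listed.
- **Aim and comparisons (Purpose, Methods).** The aim is worded as "we compared the effectiveness of peripheral nerve block" against topiramate. The planned analyses are: "Comparisons regarding VAS scores, headache frequencies, 50% responder rates and 75% responder rates were performed in between topiramate and nerve block groups".

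No safety objective is set, and the Statistical analysis section names no harms analysis.

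**The concern.** The two treatments differ in kind: one is a drug, the other an injection procedure. A clinician choosing between them will want to know how well each is tolerated as well as how well it works.

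A rule that makes stopping therapy the trigger for recording misses every reaction a patient put up with. Two arms with the same number of discontinuations could differ widely in how many patients had a reaction, and the arm with fewer discontinuations could be the one with more reactions. If the final report used the discontinuation count as evidence that one treatment was better tolerated, the data as described would not support it.

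**Working it through.** The plan gives no figure to reproduce on this point: no reaction rate, no discontinuation rate and no safety sample-size argument. The check is therefore a reading of the whole document for anything that describes recording of harms.

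1. **Reading the harms sentence.** The grammar is loose. The natural reading is that reactions which led to stopping therapy were noted. No plausible reading adds recording of reactions that did not lead to stopping.

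2. **Looking for another route.** Each described data source was compared with what a tolerability comparison would need.

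| Source described | Content named | Tolerated reactions named? |
|---|---|---|
| First neurologist's interview | Migraine features | No |
| Pre-treatment diary | Headache frequency, VAS | No |
| Records before and after therapy | VAS, headache frequency | No |
| Inpatient stay of ten days | No data items named | No |
| Post-discharge forms, 4 weeks | Items not listed | Not stated |
| Harms sentence | Reactions that stopped therapy | No |

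No method of asking about reactions and no severity grading is described for either arm.

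3. **What the described record can support.** The total is given: "Ninety chronic migraine patients with medication overuse headache were included in this study". Group sizes are not stated in the plan, but the trial will know them. With them, the number and percentage who stopped because of a reaction can be reported per arm. The chi-square test named for nominal data could be applied to those counts, although no such comparison is planned.

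4. **What it cannot support.** Patients who stopped because of a reaction are a subset of those who had one. The count in the subset sets a minimum for the full number and no more. The full number is therefore not known in either arm, and neither is the size or direction of the difference between arms.

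5. **Effect on the planned analyses.** VAS, headache frequency and the 50% and 75% responder rates come from the headache records. None of them uses the harms record, so this rule does not alter them.

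**The case against.** The strongest reply is that no planned conclusion is damaged. The document aims at effectiveness, sets no safety objective and makes no tolerability claim. Harm would arise only if a later report made a claim that this plan does not contain. That stands, and it is why the point is rated low.

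A second reply is that a recording step left undescribed may still have taken place. The contents of the post-discharge forms are not listed, and ten days of inpatient care would normally leave clinical notes. This also stands. A reader might infer that tolerated reactions went unrecorded; the document does not say so. It states which reactions were noted and is silent on the rest. The first step for a finished study is therefore to find out what exists.

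A third reply is that the text is in the past tense throughout, so a new recording rule may come too late. That may well be so, and the fix below allows for it.

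What the replies do not remove is that the harms sentence is a stated rule and more than a mere omission. A trial that follows it as written ends with a harms record that cannot compare tolerability.

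**Conclusion.** The point holds as a limit on what can be concluded about harms. As described, the data support a per-arm statement on discontinuations due to reactions. They do not support a comparison of tolerability between topiramate and nerve block. Severity is low.

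No size can be given: the document contains no reaction or discontinuation rate from which to estimate how many tolerated reactions would be missed, or in which arm.

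The conclusion rests on two assumptions: that the harms sentence means reactions which led to stopping, and that no record of tolerated reactions, made in the same way in both arms, exists beyond what is described. If such a record exists, saying so resolves the point.

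A reader might also infer that the effectiveness results are biased by this rule, or that the trial can say nothing about harms. Neither follows. The effectiveness outcomes do not draw on the harms record, and discontinuations due to reactions remain reportable.

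**What to change.** **If collection is still open.** Replace the rule with one that records every adverse reaction, its severity and whether therapy was stopped.

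- Use the same short questions in both arms at the existing form collection 4 weeks after discharge, worded to cover the inpatient stay as well. The document does not describe a data-collection contact at discharge, so the fix should not depend on one.
- Have patients complete the items themselves, returned separately from the headache form, or have the second (treating) neurologist ask them. Blinding is not stated, but answers about a drug or an injection could reveal the arm to the first neurologist, who collects the headache forms.
- Report per arm the patients with any reaction and the patients who discontinued because of one.

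The cost is one short set of items per patient at one existing contact: 90 × 1 = 90 sets. The downsides are slightly longer forms, higher reported reaction rates and recall over the inpatient stay plus follow-up, about 10 + 4 × 7 = 38 days if discharge falls on day ten.

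**If collection is finished.** First check whether tolerated reactions were recorded on the forms or in the inpatient notes, in the same way in both arms. If they were, describe how and report them per arm. If not, report only discontinuations due to reactions per arm, state the limitation and make no comparative tolerability claim. The cost is a check of existing records and one sentence in the report.
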